Analyses: Statistical analyses, such as paired t-tests or non-parametric equivalents, will be conducted to compare needle tip movement between different catheter advancement techniques. Additionally, potential confounding variables, such as participant demographics or experience level, will be accounted for in the analyses.

PARTICIPANT SELECTION CRITERIA:

We propose including 50 subjects, 18 years of age and older. Potential subjects will be approached via email listservs to inquire about potential interest in participating in the study. If they express interest, their information will be passed along to members of the study team. Consent will be obtained from the subject after the study has been explained and all questions have been answered. 50 subjects are anticipated to be enrolled.

Inclusion criteria shall be as follows:

- 1) 18 years of age or older
- 2) Willing to consent to the study
- 3) has some experience placing IV catheters

Exclusion criteria shall be as follows:

- 1) Subject refuses to consent
- 2) Younger than 18 years of age
- 3) **No experience inserting IV catheters**

After consent, the following information will be gathered from the participant:

- Demographic information (age, sex)
- Educational Status
- IV catheter experience placement

The targeted study population will include adult volunteers 18 years or older who in the course of their work or training place peripheral IV catheters. The setting in which the research will take place is the Harrell Medical Education Building (HMEB) Simulation Laboratory or in a clinical break area.

UF/Shands students and staff are included within the targeted study population as they are primarily involved in the procedure- intravenous catheter insertion- under examination. Pregnant women will be considered for this project as part of the general population and not as a targeted study population. Safeguards to minimize any coercion or undue influence include potential subjects being informed of the study via an email listserv and having them voluntarily approaching the research team indicating interest in inclusion in the research. Safeguards against coercion of students include: Investigator is not their instructor or advisor, the research is not part of a course curriculum, and there is no course credit for research participation.

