 - i. Set up the study simulator equipment in the Harrell Medical Education Building Simulation Laboratory or in a clinical break area.
 - ii. Ensure all necessary equipment, including the instrumented IV catheter and peripheral vascular access simulator, are prepared and functional.
3. Participant Orientation:
 - i. Orient participants to the study procedures, including the use of the IV simulator and catheter advancement techniques.
 - ii. Provide instructions on the three different catheter advancement techniques: self-advancement (one-handed), self-advancement (two-handed), and catheter advancement by another individual.
4. Data Collection:
 - i. Each participant will perform up to 3 IV catheter insertions using each of the specified techniques.
 - ii. Participants will use the instrumented IV catheter to insert into the peripheral vascular access simulator.
 - iii. Needle tip movement from intent of catheter advancement to 5mm of advancement off the needle will be measured with 0.2mm accuracy using the electromagnetic tracking technology of the simulator.

- iv. Data collected will include needle movement after simulated vein puncture and during catheter advancement off the needle (in mm) which will be recorded within the simulation program and output as a de-identified Excel file.
 - v. The order of catheter advancement techniques will be randomized to minimize bias.
5. Interim Analysis/Results and Conclusion (if applicable):
- i. Evaluate the study progress and any emerging trends or patterns in the data.
 - ii. Consider any necessary adjustments to study procedures or sample size based on interim findings.
 - iii. Draw conclusions based on the statistical analysis and address the study hypothesis. Discuss implications for clinical practice and potential areas for further research.

Study Visit Schedule (total time 15 minutes):

Participant arrives at the simulation setting.

Participant undergoes orientation and consent. This includes orientation to study procedure and equipment, explanation of catheter advancement techniques, and informed consent process.

Following consent, patient demographic information and educational status will be obtained. Total time required: Approximately 10 minutes.

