Participant performs IV catheter insertion using 3 techniques: 1 (Self-advancement single hand), technique 2 (Self-advancement both hands), and technique 3 (second person assisted) in randomized order. Total time required: Approximately 5 minutes. Participant's participation is concluded.

In this study, the observation to be carried out is the total distance of needle tip movement while performing intravenous catheter insertions using three different catheter advancement techniques including: Self-advancement with one hand; Self-advancement with two hands; Catheter advancement by another individual.

There is no placebo or other treatment involved in this study. The experimental control is the comparison between the three different catheter advancement techniques. Each participant serves as their own control in a within-subject, crossover design. The order in which participants perform IV catheter insertions using the different techniques is randomized, minimizing potential biases. This randomization helps ensure that the results are not influenced by the order in which the techniques are tested.

Following the consent process, the information about subjects that will be obtained from subjects is demographic data limited to age and sex as well as education status and clinical experience as well as their preferred catheter advancement technique for routine catheter placement. In addition, participants will be asked if they are familiar with the three different techniques, and what their preferred method is for difficult catheter placement. This information will be obtained by the research team prior to the start of the study at the HMEB Simulation Laboratory.

ADMINISTRATIVE RESPONSIBILITIES:

There is no Data Safety Monitoring Board (DSMB) or an oversight committee for this research project. Given the very low risk to the participants, no formal plan to monitor subject safety will be employed.

STATISTICAL METHODS, DATA ANALYSIS, AND INTERPRETATION:

In our theoretical pilot study, the mean of the needle tip movement for each group was made 3, 2, and 1 mm, respectively. We calculated the sample size to detect a mean paired difference of 0.3 (10% of group 1) with an estimated standard deviation of differences of 0.5 between the group 1 and group 3. Given a significance level of 0.05 with a power of 90%, and dropout of 10%, we finally targeted the enrollment of 30 participants.

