The Kolmogorov-Smirnov test will be performed for the normality test. For continuous variables, we will use RMANOVA if they follow a normal distribution, otherwise we will compare means with the Friedman test. Categorical data will be compared with Chi-square test. For the primary outcome, the mean lengths of the needle tip movement will be compared using the repeated-measures ANOVA or non-parametric equivalent. And then we will perform the Bonferroni correction for post hoc test. A p-value less than 0.05 was considered significant. Statistical analyses were conducted using SPSS.

The analyses will involve comparing needle tip movement measurements obtained from each participant across the three different catheter advancement techniques. Statistical software such as SPSS will be used to perform the analyses and generate descriptive statistics and inferential results. Data analyses will be conducted primarily by the research team, including [name], [name], and [name].

Interim analyses may be conducted to assess the progress of the study and evaluate any emerging trends or safety concerns. However, given the nature of the study and the minimal to no risk involved, formal stopping rules are not anticipated.

DATA STORAGE AND DE-IDENTIFICATION PLANS:

All data will be stored on departmental password protected encrypted share drives or in UF approved cloud environments (i.e. LabArchives) that only the study staff will have access to. At the conclusion of the data collection and analysis, all data will be permanently de-identified.

6. Possible Discomforts and Risks:

There are minimal (clean needle stick) risks to the participants as a result of the study. No identifiable information is being collected ameliorating any additional risk due to disclosure of identifiable information.

7. Potential Benefits:

There is no potential for direct benefits to participants beyond potentially objectively identifying a best technique for them.

The research study will benefit future populations by informing them of a technique which may indirectly improve quality of patient care and reduce IV catheter insertion failure.

8. Conflict of Interest:

No investigators have a conflict of interest beyond authorship in any resulting publication(s).

9. References:

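### Technique order is randomised, but with neither balanced orders nor a period term any common practice drift stays in the error: a cheap gain in precision, not a validity fault

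*Combined protocol and SAP*

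**What the plan says.** The protocol describes a within-person crossover of three techniques. On order, Study Procedures (Data Collection) says: "The order of catheter advancement techniques will be randomized to minimize bias". The later description of the design adds: "This randomization helps ensure that the results are not influenced by the order in which the techniques are tested". Repeats are allowed: "Each participant will perform up to 3 IV catheter insertions using each of the specified techniques".

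The analysis is described in two places. The Analyses paragraph of the Research Plan names paired t-tests or non-parametric counterparts, with adjustment for confounders; its examples are demographics and experience. The statistical methods section is more specific: "For the primary outcome, the mean lengths of the needle tip movement will be compared using the repeated-measures ANOVA or non-parametric equivalent", followed by "And then we will perform the Bonferroni correction for post hoc test". Friedman is the fallback if normality fails.

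No section says how the six possible orders are shared out among participants, and none puts period, order or sequence in a model. The movement data are to be "recorded within the simulation program and output as a de-identified Excel file"; the order actually used is not listed among the items collected.

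**The concern.** Randomising the order protects the comparison on average. It does not remove order effects from the data. If movement falls with practice on the simulator, or rises with fatigue, each participant's difference between two techniques contains a piece of that drift whose sign and size depend on the order drawn. A paired t-test, a repeated-measures ANOVA on technique alone, or a Friedman test has no term to take that piece out, so it counts as noise.

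Some drift is plausible. The experience criterion is only that the participant "has some experience placing IV catheters", and up to nine insertions (3 × 3) are made on a purpose-built simulator. At stake is power for the contrast between techniques 1 and 3, which has little slack if enrolment stops at the smaller of the two figures in the protocol. An order that is not recorded cannot be adjusted for later.

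**Working it through.** **Inputs from the statistical methods section.** Paired difference 0.3 mm between groups 1 and 3; SD of paired differences 0.5 mm; significance level 0.05; power 90%; dropout 10%; enrolment 30. The participant selection section gives 50 instead. Sidedness is not stated; two-sided is assumed. Bonferroni over three pairs gives 0.05/3 = 0.0167.

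**The plan's own figure.** n = [0.5 × (1.960 + 1.282)/0.3]² = 29.2, so 30 by the two-sided normal formula. That is before dropout; 30/0.9 = 33.3, so 34 after it. With 30 enrolled and 10% lost, 27 complete.

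**Assumption not in the documents.** A linear drift of T mm from first to third position, common to all techniques and additional to the SD of 0.5. Range shown: 0 to 0.5 mm.

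**Effect of drift on a paired difference.** Over the six orders, two given techniques are one position apart in four (contribution ±T/2) and two apart in two (±T). The added variance is (4 × T²/4 + 2 × T²)/6 = T²/2, so SD = √(0.25 + T²/2). The mean contribution is zero, so there is no bias.

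**Power without a period term** (exact noncentral t, n = 27, true difference 0.3 mm, simple random order):

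| T (mm) | SD (mm) | Power at 0.05 | Power at 0.05/3 |
|---|---|---|---|
| 0 | 0.500 | 85.1% | 70.9% |
| 0.1 | 0.505 | 84.4% | 69.9% |
| 0.2 | 0.520 | 82.3% | 67.0% |
| 0.3 | 0.543 | 78.9% | 62.4% |
| 0.5 | 0.612 | 68.8% | 50.5% |

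**Power with balanced orders and period-adjusted paired differences** (simulation, 10,000 runs per cell, 30 allocated five per order, 3 lost at random), for T = 0, 0.1, 0.2, 0.3, 0.5:
- at 0.05: 85.2, 84.9, 84.7, 84.6, 84.6%;
- at 0.05/3: 70.5, 70.0, 69.6, 69.6, 70.3%.

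A model with unstructured covariance and period gives nearly the same: 84.6-85.2% and 69.6-70.6%.

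**Cost at zero drift, n = 27.** With balanced orders, 0.1-0.3 points at 0.05 and 0.4-0.7 at 0.05/3. With simple random order, technique and period are not orthogonal and the period term costs more:
- pooled error: 1.4 points at 0.05, 2.0 at 0.05/3;
- unstructured covariance, against the paired t: 1.6 and 2.6;
- period-adjusted paired difference: 3.2 and 4.9.

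**Where the loss is small.** With n = 50 and T = 0.3, paired-t power falls only from 98.6% to 96.9% at 0.05, and from 95.8% to 91.9% at 0.05/3. With n = 27 and a true difference of 0.5 mm, power at the worst drift shown (0.5 mm) is still 98.3% and 94.6%.

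**If the 0.5 already includes drift.** Planned power is then unchanged, and removing the drift raises it. At T = 0.3 the remaining SD is √(0.25 − 0.045) = 0.453, and power at n = 27 goes from about 85% to about 91%, before deducting the two degrees of freedom.

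**The case against.** The strongest reply is that nothing in the plan is wrong. Repeated-measures ANOVA on randomly ordered treatments is valid, and the protocol says only that randomisation helps to keep order from influencing results, which is true. The drift is assumed; participants have placed IVs before and are oriented first; and the theoretical means of 3, 2 and 1 mm put techniques 1 and 3 a full 2 mm apart, where power is ample whatever is done. Randomised order does not exclude balanced blocks, and the list of adjustment variables is open-ended. All of this stands. It limits the point to an efficiency gain near the 0.3 mm difference that the sponsor chose to power for.

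Four stronger readings are tempting and are not supported.
- A reader might infer that omitting period biases the comparison or inflates type I error. Under simple random order it does neither.
- A reader might infer that the planned intervals will be too wide for their nominal level. That happens when orders are balanced and period is then left out; the plan names no balancing. It is a reason not to make only half of the change.
- A reader might infer larger gains from a model with pooled, equal-variance error. That model misstates the error of the 1-versus-3 contrast when technique variances differ, so the case should not rest on it.
- The protocol says "participants will be asked if they are familiar with the three different techniques", and a reader might infer that a period term deals with unequal familiarity. It does not: a common period effect leaves technique-specific learning where it was.

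**Conclusion.** The point holds as a cheap improvement in precision. As written, the analysis leaves any common drift in the within-person error. With 27 completers and a true difference of 0.3 mm, the loss at 0.05 is about 3, 6 and 16 points of power for drifts of 0.2, 0.3 and 0.5 mm (85.1 less 82.3, 78.9 and 68.8), and balanced orders with a period adjustment recover nearly all of it. At 0.1 mm the loss is under 1 point and there is nothing worth recovering.

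This rests on a drift that the documents do not give, on its being linear and common to the techniques, and on the SD of 0.5 mm excluding it. The conclusion that the combined change costs almost nothing does not depend on the size of the drift.

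**What to change.** 1. Allocate the six orders in balanced blocks of six (30 gives five per order; 50 gives eight or nine).
2. Record the order actually used by each participant.
3. When the parametric analysis is used, add period as a fixed effect alongside technique, taking each participant's mean per technique. Fit it through period-adjusted paired differences or a model with unstructured within-participant covariance. Keep the Bonferroni correction.
4. Leave the Friedman test in the role the statistical section gives it, and note that it carries no period term.

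The cost is an allocation list, one recorded field, a sentence or two in the analysis section and two degrees of freedom. At zero drift that is under 1 point of power if orders are balanced, but about 1.4 to 4.9 points, depending on model and significance level, if they are not. The two changes should therefore be made together. If orders have already been assigned without balance, the unstructured model loses less than the adjusted paired difference.

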Protocol

1. Title:

Investigating the Influence of Catheter Advancement Techniques on Needle Tip Movement During Intravenous Insertion

2. Investigators

PI: [name]

Co-PI: [name]

Co-Investigators:

[name]

3. Background and Significance:

Previous studies have explored various aspects of intravenous (IV) insertion techniques, focusing on factors such as needle size, angle of insertion, and patient comfort. However, there is limited research on the influence of different catheter advancement techniques on needle tip movement in the process of advancing the catheter off the needle. The proposed study aims to fill this gap by investigating whether needle tip movement during catheter advancement is affected by whether the individual performing the insertion pushes the catheter off the needle themselves (either one handed or two handed) or if the catheter is advanced off the needle by another person.

4. Specific Aims:

Aim 1: To assess the impact of three different catheter advancement techniques on needle tip movement during intravenous insertion.

Hypothesis 1: The needle tip will exhibit less movement during catheter advancement when performed by another individual compared to advancement by the inserter.

5. Research Plan:

Study Design: This study will employ a within-subject, crossover design where each participant serves as their own control. Each participant will do intravenous catheter insertions using an instrumented IV catheter and peripheral vascular access simulator using three different catheter advancement techniques: self-advancement (one-handed), self-advancement (two-handed), and catheter advancement by another individual. The order of techniques will be randomized.

Setting: The study will take place in the simulation laboratory or a clinician break area in the hospital.

Study Subjects: Participants will include adult volunteers who in the course of their work or training place peripheral IV catheters. The sample size will be determined based on power analysis to detect significant differences in needle tip movement.

Main Outcome Measures: The main outcome measure will be needle tip movement during catheter advancement, measured to within 0.2mm accuracy using a UF built IV simulator equipped with tracking technology.

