Potential subjects will be approached via email listserv advertising to inquire about potential interest in participating in the study. If they express interest, their information will be passed along to members of the study team.

Protected health information will not be accessed for this project. Measures taken to protect the confidentiality of subjects include: Computer-based files will only be made available to personnel involved in the study through the use of access privileges, passwords, and encryption; Whenever feasible, identifiers will be removed from study-related information.

Consent will be obtained by the research team including, [name] (PI), [name] (Co-PI Investigator), [name] (Co-Investigator), and [name] (Co-Investigator). Subjects will be asked to consent following recruitment and prior to commencing the study and collecting data. The Informed Consent form will be used as the summary of consent discussion. Subjects will be given the opportunity to take the consent home to discuss with family members, friends, and/or someone knowledgeable about the protocol. Coercion or unduly influencing subjects during the consent process will be minimized by emphasizing the voluntary nature of this study with additional reassurance that participants can withdraw from the study at any time without penalty. Additionally, there will be an ample opportunity for questions and no incentives will be provided through the entirety of the study.

DESIGN

STUDY PROCEDURES:

After a particular individual is identified, the research team will directly contact the subject to explain the nature of the research and the reason for contacting.

Then, an informed consent form will be provided to include details of the investigation and intended procedures. After clarifying potential questions, the treating team will be notified about the inclusion. Those that consent to participate will undergo the following procedures:

Study course:

1. Participant Recruitment and Consent:
 - i. Identify potential adult volunteers aged 18 or older involved in peripheral IV catheter insertion.
 - ii. Approach potential subjects via email listservs, inviting them to participate.
 - iii. Explain the study details and obtain informed consent from interested participants.
 - iv. Emphasize voluntary participation, the ability to withdraw without penalty, and address any questions or concerns.
2. Study Setup and Preparation:

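### The primary tests drop any participant who lacks one technique, and the plan, which budgets 10% dropout, has no rule for using partial data; the loss is small and cheap to avoid

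*Combined protocol and SAP*

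**What the plan says.** - **Primary analysis** (Statistical Methods, Data Analysis, and Interpretation): "the mean lengths of the needle tip movement will be compared using the repeated-measures ANOVA or non-parametric equivalent". If the data are not normal, "otherwise we will compare means with the Friedman test". SPSS is the named software.
- **Post hoc tests** (same section): "And then we will perform the Bonferroni correction for post hoc test". No pairwise test is named, and nothing is said about participants with incomplete data.
- **Sample size** (same section): a paired difference of 0.3 mm, with an "estimated standard deviation of differences of 0.5 between the group 1 and group 3". Then: "Given a significance level of 0.05 with a power of 90%, and dropout of 10%, we finally targeted the enrollment of 30 participants". I take groups 1 and 3 to be techniques 1 (one-handed) and 3 (second person), as numbered in the study visit schedule.
- **Withdrawal** (consent text under Participant Selection Criteria): "participants can withdraw from the study at any time without penalty".
- **Other analysis text** (Research Plan, Analyses): offers paired t-tests or non-parametric counterparts as examples of how techniques may be compared.
- **Design**: technique order is randomised, there are up to three insertions per technique, and the insertions take about 5 minutes of a single visit.

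The documents define no analysis set and give no rule for a participant with a missing technique.

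**The concern.** Repeated-measures ANOVA and Friedman both work on complete triplets. A participant with usable values for techniques 1 and 3 but none for technique 2 leaves the primary analysis, although the contrast on which the study is sized was observed in full. Because order is randomised, this can happen to anyone for whom technique 2 comes last.

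Two things are at stake. The first is precision on the 1 versus 3 contrast. The second is validity. If stopping depended on how the earlier techniques went, complete-case estimates could be biased. A likelihood analysis of all observed values would remain valid provided that stopping depended only on observed values and the model was correctly specified. With no stated rule, the choice of whom to include is also left until the data have been seen.

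**Working it through.** **Inputs from the plan:** difference 0.3 mm, SD of differences 0.5 mm, alpha 0.05, power 90%, dropout 10%, enrolment 30. **Assumed, because the plan is silent:** sidedness, the within-person correlation ρ (0.3 to 0.7), compound symmetry, and the pattern of missing techniques.

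**1. The plan's own figure.** Normal approximation: n = (SD × (z_alpha + z_power) / difference)².
- Two-sided: (0.5 × (1.960 + 1.282) / 0.3)² = 29.2, so 30 before dropout and 30/0.9 = 33.3, so 34, after it. The exact t calculation gives 32, then 36.
- One-sided: 24, then 27 (normal); 26, then 29 (exact t).

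So 30 is approached with dropout included only as a one-sided t calculation (29). It is matched exactly by the two-sided normal calculation with no dropout added. Sidedness is a separate matter; I use two-sided power below because the planned tests are non-directional.

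**2. Complete cases.** 10% of 30 is 3, leaving 27. Var(1 − 3) = 0.25/27 = 0.00926. Paired-t power is 85.1% two-sided at 0.05, 70.9% at 0.05/3 two-sided, and 91.8% one-sided at 0.05.

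**3. All observed values.** Under compound symmetry the generalised-least-squares variance can be written as 0.25/n_eff.

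(a) *The three dropouts contribute no data.* n_eff = 27; no gain.

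(b) *One stops after 0, one after 1 and one after 2 techniques, averaged over random order.* n_eff = 27 + [(2 + ρ)/(1 + ρ) + (1 − ρ)]/3.
- ρ = 0.3: 27 + (1.769 + 0.7)/3 = 27.8
- ρ = 0.5: 27 + (1.667 + 0.5)/3 = 27.7
- ρ = 0.7: 27 + (1.588 + 0.3)/3 = 27.6

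The variance falls by about 2 to 3%.

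(c) *One participant misses each technique and has the other two.* n_eff = 27 + (2 + ρ)/(1 + ρ).
- ρ = 0.3: 28.77, variance ratio 1.066
- ρ = 0.5: 28.67, variance ratio 1.062
- ρ = 0.7: 28.59, variance ratio 1.059

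The variance falls by about 6% (for example, 1 − 1/1.062 = 5.8%).

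(d) *Ceiling: all three miss technique 2 only.* Each then counts in full for 1 versus 3, so n_eff = 30 and the variance falls by 1 − 27/30 = 10%.

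**4. Power for 1 versus 3, two-sided 0.05.** 85.1% (n = 27), 86.4% (28), 87.7% (29), 88.8% (30). The most that can be gained is 88.8 − 85.1 = 3.7 points. At 0.05/3 the range is 70.9% to at most 76.7%.

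**5. Available pairs only.** If each dropout stops after 0, 1 or 2 techniques with equal chance and all orders are equally likely, a dropout has both techniques 1 and 3 with probability 1/3 × 1/3 = 1/9. That is 3/9 = 0.33 participants recovered per 30. Simulated power, with the number of dropouts varying around 3, moves from 84.9% to 85.4%.

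**6. At the 50 enrolled given under Participant Selection Criteria.** 45 complete gives 97.6%, and at most 98.6% if all 50 are recovered.

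**The case against.** The strongest case against is that this is a minor wording gap.

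- *The dropout allowance already covers the loss.* Budgeting 10% and analysing completers is consistent. That stands as to numbers, but the allowance does not say whether valid partial data are used.
- *Dropouts may leave no data.* Subjects may take the consent form home, so someone could consent and never attend. This stands. A reader might infer from the single 15-minute visit that most dropouts would stop partway, but the documents do not describe who drops out.
- *A whole technique will rarely be missing.* The task is short and allows up to three insertions per technique. If repeats are done, one unusable reading would not remove a technique. This stands and limits the likely size.
- *The 1 versus 3 comparison may not lose anyone.* A reader might infer that the Bonferroni comparisons inherit the complete-case set. The plan does not say so, and the paired t-tests mentioned in the Research Plan would keep anyone with both techniques. But the statistical methods section does not name them as the post hoc method, and the omnibus test drops these participants in any case.
- *There is no evidence of bias.* Correct: the documents give no sign that stopping would depend on results. The bias argument is conditional.

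**Conclusion.** The point holds at small size. The named primary tests discard partial data that the plan's own dropout allowance makes possible, and no rule offsets this. With 3 of 30 incomplete, the variance reduction for 1 versus 3 is none, about 2 to 3%, or about 6% under the three patterns set out above. The extreme is 10%, if every dropout misses technique 2 alone, and it is this extreme that gives the ceiling of 88.8% power. These figures assume compound symmetry and a correlation of 0.3 to 0.7; the missing-data patterns are mine, not the plan's.

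A reader might go further and conclude that the powered contrast is certain to lose participants, that the result will be biased, or that a higher rate such as 20% incomplete should be planned for. The documents support none of these. They leave the pairwise test open, give no mechanism for outcome-related stopping, and state 10%. The plan is not invalidated; a better analysis is available at almost no cost.

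**What to change.** In the statistical methods section:

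1. Make the primary analysis a linear mixed model fitted by REML (SPSS MIXED), with technique as a fixed effect and repeated measures within participant, using every observed technique value. Specify an unstructured covariance, with compound symmetry if that does not converge. Take the Bonferroni-adjusted contrasts, including 1 versus 3, from this model.
2. If the non-parametric branch is used, run Bonferroni-adjusted Wilcoxon signed-rank tests on all available pairs, including 1 versus 3. Without this, Friedman would still drop the same people.
3. Report the complete-case repeated-measures ANOVA or Friedman test as a sensitivity analysis.
4. Define the analysis set, and state that data already collected from participants who stop early are kept as far as the consent allows.

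**Cost:** wording only. There is no extra enrolment, data collection or software. The downside is that the model relies on a covariance structure and a missing-at-random assumption. The available-pair signed-rank tests recover participants but do not give that missing-at-random protection.

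### Bonferroni after a three-technique omnibus test is valid but more conservative than 5% family-wise control requires; Holm or a closed test would recover power

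*Combined protocol and SAP*

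**What the plan says.** The Statistical Methods section says that for the primary outcome "the mean lengths of the needle tip movement will be compared using the repeated-measures ANOVA or non-parametric equivalent", and continues: "And then we will perform the Bonferroni correction for post hoc test". The threshold is p < 0.05. The section does not say whether the pairwise tests depend on a significant omnibus result, or how many pairs the correction covers.

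Section 5 (Analyses) describes the comparison differently, with no omnibus test and no correction: "Statistical analyses, such as paired t-tests or non-parametric equivalents, will be conducted to compare needle tip movement between different catheter advancement techniques".

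The sample size rests on one contrast, a mean paired difference of 0.3 "with an estimated standard deviation of differences of 0.5 between the group 1 and group 3". Read against the numbering in the visit schedule, that is one-handed against assisted. The target follows: "Given a significance level of 0.05 with a power of 90%, and dropout of 10%, we finally targeted the enrollment of 30 participants". The Participant Selection Criteria give 50 subjects instead. Hypothesis 1 (Section 4) is that movement is less when another person advances the catheter than when the inserter does.

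**The concern.** The omnibus test can show that the techniques differ somewhere, but not that assisted advancement moves the needle tip less. Hypothesis 1 is decided by assisted against each self-advancement technique, and those are the tests to which Bonferroni applies.

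With three means, any two pairwise equalities imply the third. The only intersection of pairwise null hypotheses is therefore the global null. By the closed testing principle, a valid 5% omnibus test followed by unadjusted 5% pairwise tests holds the family-wise error at 5% in the strong sense. Dividing alpha as well buys no error control that the plan needs. What is at stake is power: a real difference could be missed that the same data would show under the same error guarantee.

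**Working it through.** **Inputs from the documents.** Paired difference 0.3 mm; SD of the one-handed minus assisted difference 0.5 mm; alpha 0.05; power 90%; dropout 10%; enrolment 30 (Statistical Methods) or 50 (Participant Selection Criteria).

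**Assumptions not in the documents.** Bonferroni over all three pairs (0.05/3 = 0.0167 each, two-sided); pairwise tests gated on the omnibus, unless stated otherwise; SD 0.5 mm for the other two paired differences; several positions for two-handed.

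**The plan's own figure.** n = ((z_alpha + z_power) × SD/difference)².
- Two-sided: ((1.960 + 1.282) × 0.5/0.3)² = 29.2, so 30 before dropout and 34 after. The exact paired t-test gives 32 and 36.
- One-sided: ((1.645 + 1.282) × 0.5/0.3)² = 23.8, so 24 and 27. The exact paired t-test gives 26 and 29.

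So 30 is met approximately by a one-sided paired t-test with dropout, or by a two-sided normal approximation without dropout. No version includes a multiplicity allowance.

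**Completers.** 30 × 0.9 = 27; 50 × 0.9 = 45.

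**Powered contrast at 27 completers, exact paired t-test.** Noncentrality = (0.3/0.5) × √27 = 3.12. Two-sided power is 85% at 0.05, 76–77% at 0.025 and 71% at 0.0167. Reaching 90% at 0.0167 takes 41 completers (41/0.9 = 45.6, so 46 enrolled).

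**Comparison of procedures at 27 completers.** Simulation with a Greenhouse-Geisser-corrected omnibus F, assisted mean 0 and one-handed mean 0.3 mm:

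| Claim | Two-handed mean | Omnibus + Bonferroni | Holm, no omnibus | Closed test |
|---|---|---|---|---|
| One-handed vs assisted | 0.15 | 69% | 72% | 76% |
| One-handed vs assisted | 0.3 | 71% | 75% | 82% |
| One-handed vs assisted | 0 | 70–71% | 74–75% | 82% |
| Both assisted contrasts | 0.3 | 57% | 64% | 75–76% |

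With two-handed at 0.225 mm, the chance of showing both assisted contrasts goes from 36.4% to 56.2% under the closed test.

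**Family-wise error at 27 completers.** Equal variances: closed test 4.7–5.0%; omnibus plus Bonferroni about 3.4–3.5% under the global null and 1.6–1.7% with one equal pair. Unequal variances: closed test 5.8–5.9% with an uncorrected F, 4.8–4.9% with Greenhouse-Geisser.

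**Larger enrolment.** On the powered contrast the closed test gains about 2–4 points at 45 completers and 1–3 at 50. The chance of showing both assisted contrasts with two-handed midway still rises from 36.6% to 54.4% at 50.

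**Theoretical means of 3, 2 and 1 mm.** Power is about 100% under every procedure, so there is no gain.

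**Friedman and Wilcoxon, 27 completers, equal variances.** One-handed vs assisted: gated Bonferroni 56–62%, closed test 61–70%, ungated Bonferroni about 68%. On this route the Friedman gate itself costs power.

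**The case against.** The plan's procedure is conventional and controls error; nothing in it inflates a claim. That stands, and it limits the point to efficiency.

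A reader might infer that the plan corrects twice. The documents do not establish this. The order of the two sentences suggests a gate, but none is stated. Without one there is a single correction, and nearly all the loss comes from the 0.05/3 level: with the F test, gating costs at most about 2 points. Nor is it then true that Bonferroni can never reject where the closed test does not. With two-handed midway at 27 completers, that happened for the powered contrast in roughly 1.4% of simulated trials, although average power still favoured the closed test (77% against 71%, uncorrected F).

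The divisor of three is also inferred. Hypothesis 1 needs only the two assisted contrasts. At 0.025 each, one-handed versus assisted has about 76–77% power at 27 completers, so the closed test gains only about 0–5 points.

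A reader might also quote a loss of 7 to 20 points without conditions. The documents do not support that. The upper end is for showing both assisted contrasts, whereas the plan powers only one. The range needs enrolment of 30, while another section gives 50. At 45 completers the planned rule already has about 93% power for the powered contrast, above the 90% target.

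Finally, the closed test needs a sphericity correction that the plan does not mention, and it yields no matching simultaneous intervals. Both are fair costs.

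**Conclusion.** The point holds as an efficiency improvement. Under the stated assumptions with 27 completers and the repeated-measures ANOVA route, the closed test raises power for one-handed versus assisted from about 69–71% to 76–82%, and Holm raises it to 71–75%. For both assisted contrasts, if only assisted differs, the figures are about 57% as planned, 75–76% closed and 64% with Holm. The size depends on enrolment, on the number of pairs corrected, on the other two SDs and on where two-handed lies. At 45–50 completers the benefit on the powered contrast is small, though it can remain large for showing both contrasts. That the closed test is valid with three means is a matter of logic and does not depend on these assumptions, provided the omnibus test itself is valid.

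**What to change.** At minimum, replace Bonferroni with Holm over the stated pairs. Holm rejects everything Bonferroni rejects, and sometimes more, at the same family-wise error, with or without an omnibus gate.

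For more power, prespecify wording such as: *The omnibus test (sphericity-corrected F, or Friedman) is carried out at 0.05. If it is significant, each of the three pairwise comparisons (paired t-test, or Wilcoxon signed-rank) is tested at 0.05 without further adjustment. If it is not significant, no pairwise difference is claimed.*

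If the sponsor does not intend a gate, Holm is the safer choice on the non-parametric route, because the Friedman gate can cost more than the unadjusted level returns.

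In either case, state the number of pairs and whether a gate applies, align the Analyses paragraph in Section 5, and reconcile 30 with 50, since that settles how much is gained.

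The cost is a short rewording before the needle-movement data are analysed, and no extra participants. With the closed test, ordinary 95% intervals would be reported and labelled as unadjusted, and the sphericity correction becomes essential.
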